**BOTOX® (Botulinum Toxin Type A)**  
Purified Neurotoxin Complex

## 10.2. Populations for Analyses

The analysis populations will consist of participants as defined below:

**Table 10-2 Analysis Populations**

Population	Definition	Study Treatment
Screened	All screened participants who sign informed consent	—
Enrolled	All the participants who sign informed consent and screened with eligibility verified	—
Intent-to-treat (ITT)	For Stages 1 and 2, the ITT populations will include all randomized participants. The efficacy data will be analyzed as randomized using the ITT populations for Stages 1 and 2 separately. The primary efficacy analysis will be performed in Stage 2 on the ITT population when all study participants reach Week 12.	Randomized treatment assignment
Safety	For Stages 1 and 2, the safety population will include all participants enrolled in this study who received the study treatment.	Actual treatment received

## 10.3. Statistical Analyses

The 2-stage study design described in [Section 5.1](#) was selected to satisfy two separate goals in a specific sequence. The focus of Stage 1 of the study is establishing safety whereas Stage 2 is intended to identify the most efficacious dose. For Stage 1, the analyses of safety endpoints will take primacy; analysis of efficacy endpoints will be supplemental. For the prior reason, efficacy analyses for Stage 1 will be descriptive in nature only; no inferential testing will be performed.

The statistical analysis plan (SAP) will be developed and finalized before database lock for stages 1 and 2, separately. SAP will describe the participant populations to be included in the analyses, and procedures for accounting for missing, unused, and spurious data.

This section is a summary of the planned statistical analyses of the primary and secondary endpoints for Stage 2

### 10.3.1. Key Statistical Methodology

The methodologies defined below apply as specified to individual endpoints.

**Table 10-3 Statistical Methodology**

Methodology	Description
Categorical counts	
 
Number of participants in individual categories           
 
Participants with <math>\geq 1</math> qualifying event counted once per individual category
 
 
 

Categorical descriptives	
 
Number and percentage of participants in individual categories           
 
Participants with <math>\geq 1</math> qualifying event counted once per individual category
 
 
 
N1 if percentage denominator <math>\neq</math> number of participants in the population (standard)
 

**BOTOX® (Botulinum Toxin Type A)**  
**Purified Neurotoxin Complex**

Methodology	Description
	percentage denominator) 
 
○ N1 = participants with nonmissing baseline value
 

PCS descriptives	
 
• Number and percentage of participants meeting potentially clinically significant (PCS) criteria 
 
○ Participants with <math>\geq 1</math> qualifying event counted once per PCS category
 
 
 
• Percentage denominator = number of participants with nonmissing baseline and <math>\geq 1</math> nonmissing postbaseline assessment 
 
○ Unevaluable assessments considered missing
 
 
 

Event descriptives	
 
• Number and percentage of events in individual categories 
 
○ Events counted individually for each instance
 
 
 
• Percentage denominator = total number of events
 

Shift analysis	
 
• Number and percentage of participants in individual baseline and postbaseline categories
 
• Percentage denominator = number of participants in individual baseline categories
 
• N1 = participants with nonmissing values at both baseline and the specified postbaseline analysis visit
 

Continuous descriptives	
 
• N1, mean, SD, median, minimum, maximum
 
• N1 = participants with nonmissing value
 

CFB descriptives	
 
• Continuous descriptives for baseline, postbaseline, and change from baseline (CFB) values
 
• N1 = participants with nonmissing values at baseline visit
 
• Missing values replaced by the last observation carried forward (LOCF)
 

CFB ANCOVA	
 
• Continuous descriptives and standard error (SE) for baseline, postbaseline, with LOCF, and CFB values
 
• Estimates derived from mixed model for CFB value controlling for factors (treatment group and stratification variables) and covariates (baseline value) 
 
○ Least squares (LS) means and standard errors
 
○ LS mean differences, standard errors, and 95% confidence intervals vs placebo
 
○ P-values from contrast t-test comparing [BOTOX dose groups vs placebo]
 
 
 
• N1 = participants with nonmissing values at baseline
 

CFB ANCOVA Sensitivity	
 
• Continuous descriptives and standard error (SE) for baseline, postbaseline with only observed values, and CFB values
 
• Estimates derived from mixed model for CFB value controlling for factors (treatment group and stratification variables) and covariates (baseline value) 
 
○ Least squares (LS) means and standard errors
 
○ LS mean differences, standard errors, and 95% confidence intervals vs placebo
 
○ P-values from contrast t-test comparing [BOTOX dose groups vs placebo]
 
 
 
• N1 = participants with nonmissing values at both baseline and the specified postbaseline analysis visit
 

**BOTOX® (Botulinum Toxin Type A)  
Purified Neurotoxin Complex**

Methodology	Description
Responder	
 
• Categorical descriptives for responders and nonresponders           
 
◦ Nonresponders include:               
 
▪ Participants who do not meet responder criteria
 
▪ Participants with no postbaseline values
 
 
 
 
 
• 95% confidence interval for the proportion
 
• Estimates derived from Cochran-Mantel-Haenszel (CMH) model controlling for stratification factors           
 
◦ Mantel-Haenszel (MH) odds ratios (ORs) and confidence intervals vs placebo
 
◦ P-values for the adjusted odds ratio of BOTOX dose groups vs placebo
 
 
 
• N1 = all participants unless otherwise specified
 

Time-to-event	
 
• Categorical descriptives for participants with events and censoring           
 
◦ Censoring includes:               
 
▪ Participants who do not meet event criteria
 
▪ Participants with no postbaseline values
 
 
 
 
 
• Quartiles and 95% confidence intervals for median derived from Kaplan-Meier (KM) nonparametric model using log-log transformation of survival function
 
• Estimates derived from log-rank model controlling for stratification factors           
 
◦ P-values comparing BOTOX dose groups vs placebo
 
 
 
• N1 = all participants unless otherwise specified
 

KM figure	
 
• Step-function figure of [survival function/cumulative distribution function [1 – survival function]] estimates with censoring indicators, derived from KM nonparametric model
 

ANCOVA = analysis of covariance; ANOVA = analysis of variance; CFB = change from baseline; Cochran-Mantel-Haenszel; KM = Kaplan-Meier; LOCF = the last observation carried forward; TTE = time-to-event.

### 10.3.1.1. Hypothesis

For the primary efficacy analysis, the null hypothesis is that there is no difference between each BOTOX and Hydrogel admixture group and placebo and Hydrogel admixture group as measured by the change from baseline in daily average number of urinary incontinence episodes at Week 12 post-study treatment. The alternative hypothesis is that there is a difference between each BOTOX and Hydrogel admixture group and placebo and Hydrogel admixture group as measured by change from baseline in daily average number of urinary incontinence episodes at Week 12.

### 10.3.1.2. Methods of Analysis

In general, baseline is defined as the last nonmissing assessment before Day 1. Continuous variables will be summarized with descriptive statistics (sample size, mean, median, standard deviation, minimum, and maximum values). Categorical variables will be summarized with frequency distributions (counts and percentages).

BOTOX® (Botulinum Toxin Type A)  
Purified Neurotoxin Complex

### 10.3.2. Efficacy Analyses

#### 10.3.2.1. Collection and Derivation of Primary and Secondary Efficacy Measures

Primary Measure (Number of urinary incontinence episodes [UIE] per day):

UIE will be recorded in a 3-day bladder diary and calculated as the average number of episodes per day over a consecutive 3-day period.

The participant's baseline number of UIE will be the average from the 3 reported consecutive days immediately prior to randomization.

Secondary Measures (Number of micturition episodes per day and Volume voided per micturition):

Both secondary measures will be recorded by the participant on the same diary. Number of micturition episodes per day will be calculated based on a consecutive 3-day average. The volume voided per micturition will be calculated from the total urine volume from micturitions (toilet voids or catheterizations) over one 24-hour period during the 3-day participant bladder diary divided by the number of micturitions in the same 24-hour period.

#### *Missing Data*

Every effort will be made to obtain required data at each scheduled evaluation from all participants who have been enrolled. The last observation carried forward (LOCF) imputation method will be used for the primary analysis in Stage 2. Sensitivity analyses will be performed using only observed data.

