The dose-finding study (Study 191622-077) evaluated a range of BOTOX doses (50 U, 100 U, 150 U, 200 U, and 300 U) versus placebo (N = 313). The phase 3 program included 2 identical pivotal phase 3 studies in OAB patients who were not adequately managed with anticholinergic therapy (Study 191622-095, N = 557 and Study 191622-520, N = 548). Patients in both studies received 100 U BOTOX or placebo administered as intradetrusor injections via cystoscopy. Patients could receive an additional treatment of 100 U BOTOX if pre-specified retreatment criteria were fulfilled and could enter a long-term extension study (Study 191622-096, 3 years duration) in which they could receive multiple treatments of BOTOX (100 U or 150 U BOTOX). Both pivotal phase 3 studies achieved both co-primary efficacy endpoints of significant reductions in urinary incontinence at Week 12 and a significantly higher proportion of patients reporting their condition as improved or greatly improved on the Treatment Benefit Scale (TBS) (Nitti 2013a; Chapple 2013). In addition, all secondary endpoints were met in both pivotal studies, which included OAB symptoms and other HRQL parameters. The duration of effect of BOTOX, based on the first 100 U BOTOX treatment cycle phase 3 data integrated with the long-term extension study data, was approximately 6 months.

With respect to safety, adverse events were primarily local adverse events related to the urinary tract, in particular, urinary retention and UTI. Treatment with 100 U BOTOX was associated with a transient increase in PVR urine volume with a peak effect by Week 2, although majority of the patients did not have an increase greater than 100 mL.

A consistent efficacy and safety profile has been demonstrated with repeat BOTOX treatment with peak efficacy between Week 6 and Week 12 post injection. The reductions from baseline in urinary incontinence episodes remained similar over repeated BOTOX treatments, as did the improvement in HRQL. The most common adverse events remained urological (eg, UTI and urinary retention), and the incidence of such adverse events did not increase with repeated BOTOX treatment.

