**BOTOX Intravesical Instillation:**

A double-blind, randomized, pilot study with intravesical instillation of BOTOX and Hydrogel in OAB patients has been completed (Krhut 2016). A total of 39 females with OAB symptoms were randomized for the study into 4 groups, receiving 50 mL intravesical instillations [REDACTED]

[REDACTED] Key endpoints of the study where the number of urgency grade 3 + 4 episodes/72 h, number of leakage episodes/72 h (both recorded in a 3-day bladder diary), OAB

**BOTOX® (Botulinum Toxin Type A)  
Purified Neurotoxin Complex**

Questionnaire (OAB-q) total score and Patient Perception of Bladder Condition (PPBC) scale total score both recorded immediately before treatment and 1 month after treatment. Analysis of bladder diary and self-assessment questionnaire data showed superiority of [REDACTED] 200 U BOTOX over all other groups for number of urgency grade 3<+< 4 episodes/72 h, number of leakage episodes/72 h, Overactive Bladder Questionnaire (OAB-q) total score and PPBC total score. DMSO treatment was superior over all other groups with respect to the number of nocturia episodes/72 h. No serious adverse events were observed during the study. In only one instance (an episode of UTI) was the adverse event considered to be related to the study procedure. No significant effects on the ability to empty the bladder (increase in PVR or decrease in bladder contractility index [BCI]) were recorded. Overall, the results of this pilot study demonstrated that intravesical instillation of BOTOX with Hydrogel was safe and tolerable with efficacy potentially sustained over the course of a few weeks.

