10.1 PRIMARY EFFICACY VARIABLE

The primary efficacy variable is the change from baseline in the average number of urinary incontinence episodes (UIEs) per day. The primary timepoint is week 12.

The number of UIEs per day will be recorded in the participant bladder diary over 3 consecutive days at any time during the screening period for the screening diary, and over 3 consecutive days during the week prior to each post baseline visit. The average number of UIEs per day will be calculated as the total number of episodes recorded in the 3-day bladder diary divided by the total number of valid diary days (see [Section 15.2](#)). Calculation of averages will employ available “valid diary days” data without imputation. If no “valid diary days” data are available for the consecutive 3-day period, that average will be considered missing for that participant. The last-observation-carried-forward (LOCF) approach will be used to impute missing postbaseline average values.

For the primary efficacy analysis, the null hypothesis is that there is no difference between each (BOTOX and Hydrogel admixture group) and (placebo and Hydrogel admixture) in the mean change from baseline in daily average number of UIEs at week 12. The alternative hypothesis is that there is a difference between each (BOTOX and Hydrogel admixture group) and (placebo and Hydrogel admixture group) in the mean change from baseline in daily average number of UIEs at week 12.

The hypotheses will be tested using an ANCOVA model with baseline value as covariate and treatment group and sex (male, female) as factors. Pairwise comparisons will be performed for each BOTOX group versus placebo using t-tests of the least square means from the ANCOVA model. The stratification factor of baseline UUIEs (≤ 9 or > 9 episodes/day) is not included in the model due to a very high correlation between UIEs and UUIEs (Pearson’s correlation coefficient = 0.97 based on phase 2 data (191622-077 study)).

A sensitivity analysis of the primary efficacy variable will be performed using the same ANCOVA model discussed above. This will be based on observed data only (i.e. no LOCF imputation of missing postbaseline average values).

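### The Stage 2 primary analysis carries the last diary forward to Week 12, which the documents do not justify for instillation, and no visible analysis uses the earlier diaries under missing at random

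*Protocol*

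**What the plan says.** Protocol 10.3.2.1, Missing Data: "The last observation carried forward (LOCF) imputation method will be used for the primary analysis in Stage 2". Stage 2 SAP 10.1 does the same for missing post-baseline UIE averages. An average is missing only when the 3-day period has no valid diary day. Diaries are kept "over 3 consecutive days during the week prior to each post baseline visit". The analysis windows in SAP 15.1 are Week 2 (Days 2-29), Week 6 (Days 30-64) and Week 12 (Days 65-99). The value carried to Week 12 is therefore the Week 6 average or, failing that, the Week 2 average.

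The primary model is an ANCOVA with baseline, treatment and sex. The sensitivity analysis repeats it, and the SAP says: "This will be based on observed data only (i.e. no LOCF imputation of missing postbaseline average values". Protocol Table 10-3 calls the model mixed, but it lists only treatment, stratification variables and baseline. With no visit term or covariance structure, it is not a repeated-measures analysis.

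On the time course, Protocol 3.2.4 gives two kinds of evidence:
- **Injection:** "peak efficacy between Week 6 and Week 12 post injection", and a duration of effect that, "integrated with the long-term extension study data, was approximately 6 months".
- **Instillation:** one pilot study in 39 women. The only assessment time given is in "both recorded immediately before treatment and 1 month after treatment", and its conclusion is hedged: "with efficacy potentially sustained over the course of a few weeks".

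Protocol 10.3 leaves to the SAP the "procedures for accounting for missing, unused, and spurious data". Stage 2 SAP pages 17-19 and the content of section 15.2 are not shown, so this point concerns the visible text only.

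**The concern.** Carrying a value forward assumes that a participant's response stays constant after the last diary. The injection data cannot simply be borrowed to support this: the route differs, and Protocol 5.5 itself says that penetration may be significantly lower by instillation. Even for injection, a carried Week 2 value could precede the peak. The pilot neither shows nor excludes waning by Week 12.

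The observed-case ANCOVA does not fill the gap. It discards the Week 2 and Week 6 outcomes of anyone missing Week 12, so it is biased when loss depends on those outcomes. Both planned estimates can therefore be wrong, with no visible estimate that uses the earlier diaries under missing at random to set beside them. The Week 12 dose-placebo contrasts feed phase 3 planning (SAP 12.0), so the size and ranking of the dose effects are what is at stake.

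**Working it through.** **1. The plan's own figures (Protocol 10.1, Table 10-1).** Difference 1.8, SD 3.5, two-sided alpha 0.05, 50 evaluable per arm. SE = 3.5 x sqrt(2/50) = 0.70 and noncentrality = 1.8/0.70 = 2.57 on 98 df. Power is 72.1%, matching the stated 72%. 50/0.95 = 52.6, so 53 per arm; 5 x 53 = 265. At 5% attrition, 0.05 x 53 = 2.65 participants per arm lack Week 12.

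**2. Yardstick.** With 53 per arm, SE = 3.5 x sqrt(2/53) = 0.68. If baseline correlates 0.4 with change (assumed), SE = 0.68 x sqrt(1 - 0.16) = 0.62.

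**3. Hand calculation, loss unrelated to outcome and equal by arm.** Bias = m2 x (d2 - d12) + m6 x (d6 - d12). Here d is the true BOTOX-placebo difference at Weeks 2, 6 and 12, and m2 and m6 are the fractions carrying Week 2 and Week 6. Positive bias overstates the benefit. Assume half the losses fall at each point.

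At 20% missing:
- Flat (1.8, 1.8, 1.8): 0
- Rising (0.9, 1.35, 1.8): 0.10 x (-0.9) + 0.10 x (-0.45) = -0.135
- Falling (1.8, 1.8, 0.9): 0.20 x 0.9 = +0.18
- Gone (1.8, 1.8, 0): 0.20 x 1.8 = +0.36

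At 5% each is a quarter of that: 0, -0.03, +0.045 and +0.09.

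**4. Simulation with loss depending on earlier response.** 50,000 two-arm trials per scenario, 53 per arm, SD 3.5. Assumed: between-visit correlation 0.6, baseline-change correlation 0.4, and monotone loss that is likelier with a poor last response. Both ANCOVAs adjust for baseline and treatment; sex is omitted. Monte Carlo error is about 0.003. Entries are bias in episodes/day for dropout log-odds slopes of 0 / 0.5 / 1 per SD.

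| Course | LOCF, 5% missing | LOCF, 20% missing | Observed-case, 20% missing |
|---|---|---|---|
| Flat | 0.00 / +0.01 / +0.03 | 0.00 / +0.02 / +0.07 | 0.00 / -0.04 / -0.11 |
| Rising | -0.03 / -0.03 / -0.01 | -0.14 / -0.12 / -0.08 | 0.00 / -0.03 / -0.07 |
| Falling | +0.05 / +0.05 / +0.06 | +0.18 / +0.18 / +0.22 | 0.00 / -0.04 / -0.11 |
| Gone | +0.09 to +0.10 | +0.34 to +0.36 | not tabulated |

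For the first three courses at 5%, observed-case bias is 0.00 to -0.04. The largest LOCF bias there is 0.06/0.62, about 0.1 SE.

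At 20% the two planned estimates differ by 0.18 / 0.22 / 0.33 (falling), 0 / 0.06 / 0.18 (flat) and 0.14 / 0.09 / 0.01 (rising). In the last rising case they agree to 0.01 while both are too low, so agreement between them is not reassurance.

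**5. False rejection when the Week 12 effect is truly zero (gone).** By hand, with SE 0.68: bias 0.09 gives 5.2% and bias 0.36 gives 8.2%. The simulation, with baseline adjustment, gives 5.3-5.4% at 5% missing and 8.5-8.9% at 20%.

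**6. Robustness.** With correlation 0.4 / 0.8 (20% missing, slope 0.5), LOCF bias is +0.03 / +0.01 (flat), -0.11 / -0.12 (rising) and +0.19 / +0.17 (falling). A likelihood-type estimate from all three diaries stays within 0.003 of the truth in step 4, but by construction, since loss there was missing at random. If the later losses instead depend on the unseen Week 12 change (slope 1, 20%), biases for flat / rising / falling are:
- Likelihood-type: -0.07 / -0.07 / -0.04
- LOCF: +0.01 / -0.13 / +0.18
- Observed-case: -0.16 / -0.14 / -0.10

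**The case against.** The best defence is size. The only loss rate in the documents is 5%, and there the effect is slight. Treatment is a single instillation, Protocol 8.2 asks for at least 12 weeks of follow-up and an exit assessment, the Week 12 window is wide, and one valid diary day is enough for an average. Larger biases need an assumed 20% and an assumed time course. All of this stands, except that 5% describes attrition: a retained participant without a valid diary day is also missing, so diary missingness can exceed it.

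It is also fair that no method is safe under every mechanism. LOCF is nearest the truth for a flat course in the last part of step 6. This supports keeping LOCF in the plan, but does not supply the missing estimate. By-visit observed summaries will show the course only among those still observed.

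Three stronger readings are tempting but not supported:
- **LOCF inflates the BOTOX effect.** That requires waning, which the documents neither show nor exclude. With a rising course the bias runs against BOTOX.
- **Nothing planned is valid under missing at random.** The observed-case ANCOVA is valid in the narrow case where missingness depends only on baseline, treatment and sex.
- **The SAP silently drops LOCF for the secondary endpoints.** Table 10-3, applied through the endpoint table, can be read as requiring it. But the protocol's Missing Data paragraph limits LOCF to the primary analysis, the endpoint table names it only for UIE, and the SAP 10.0 sentence limiting imputation to the primary variable allows exceptions stated elsewhere, while pages 17-19 are not shown. This is an ambiguity to clarify.

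**Conclusion.** The point holds as an inexpensive improvement, and it does not show that the planned result would be wrong. LOCF rests on a constancy assumption that the documents do not establish for instillation, and the one visible alternative ignores the earlier outcomes of those missing Week 12. At the planned 5% the consequence is small, about 0.09 episodes/day even if the effect has gone by Week 12. It becomes material only with more missing diaries, and its sign depends on an unknown time course. The 20% rate, courses, correlations, timing of loss and dropout mechanisms are assumptions. The sample size, SD, difference and 5% attrition come from the documents. Undisclosed SAP text could already contain a further analysis.

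**What to change.** Estimate each Week 12 dose-placebo contrast by an MMRM on the observed Week 2, 6 and 12 averages. Include treatment, visit, treatment-by-visit, baseline, baseline-by-visit and sex, with unstructured covariance. Preferably make this the primary analysis and keep the LOCF and observed-case ANCOVAs as sensitivity analyses. If the sponsor keeps LOCF as primary for continuity with the protocol, prespecify the MMRM as a sensitivity analysis.

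Report Week 12 diary missingness by arm. Because MMRM assumes missing at random, a delta-adjusted check is useful, but its range must be stated: for example, worsening imputed BOTOX-arm values by 0 to 1.8 episodes/day, the design difference.

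Record the change in Stage 2 SAP 10.1 and 16.0, and in the protocol's Missing Data paragraph, Table 10-3 and endpoint table. SAP 16.0 could also say whether LOCF applies to the secondary endpoints; no change to their models is needed.

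The cost is a small protocol and SAP edit plus standard programming on diaries already scheduled. No new data are needed, and the planned 53 per arm stands. The downside is less direct comparability with any earlier LOCF-based analyses, which retaining the LOCF analysis covers.
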